### **Descriptive Analyses**

### Estimating the Cumulative Distribution of a Right-Censored Outcome

Following the notation by Cole et al (Cole et al, 2015) and Brookhart (Brookhart, 2019), let  $T_i$  be the continuous random variable for the time from treatment initiation to acute MI

for the  $i^{th}$  patient, and let *t* represent the realization (ie, a specific value) of  $T_{i.}$  The cumulative incidence (ie, risk) of the acute MI outcome at time *t* is the complement of the Kaplan-Meier survival function,

$$R(t)=1-S(t)=\Pr(T_i < t).$$

The entire function over time is of interest, but the cumulative incidence of acute MI at times t=6 months, t=1 years, and t=2 years after the start of treatment will also be estimated.

The naïve, unadjusted cumulative incidence of the outcome, R(t), subject to rightcensoring by *C*, can be conveniently estimated with the following estimating function:

$$\widehat{Pr}(T < t) = \frac{1}{n} \sum_{i=1}^{n} \frac{\Delta_i I(T_i < t)}{Pr(\Delta_i = 1)},$$

where  $\Delta = l(T < C)$  is an indicator that the patient was uncensored. In the denominator  $Pr(\Delta_i = 1)$  implies that censoring is non-informative (ie,  $C \perp T$ ), and, so, the cumulative incidence curve that is initially estimated assumes that censoring occurs at random.

In addition to estimating the cumulative incidence, the incidence rate, overall, and by selected baseline characteristics, with 95% confidence intervals based on the Poisson distribution, will also be estimated.

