The naïve, unadjusted cumulative incidence (ie, risk) of hypertension, acute MI, and stroke will be estimated in the following new user cohorts: 1) erenumab-aooe, 2) other mAbs targeting the CGRP pathway, (2) select SOC migraine preventive medications (anti-epileptics), and (3) onabotulinumtoxinA.

Next, the overlap of the propensity score across treatment groups will be evaluated, the mean standardized difference for all variables included in the propensity score model will be assessed, and a determination will be made on whether null findings are or are not estimated for the negative control outcomes chosen for the study. Comparability between erenumab-aooe and each of the other treatment cohorts will be evaluated separately and each of the comparative analyses will be gated. Specifically, the decision to move forward with the comparative analyses for either the acute MI or the stroke outcome will be made after assessment of covariate balance across treatment groups, whether the negative control outcomes showed treatment associations within the accepted bounds around the null, and sufficient sample size to detect a risk ratio of 2.0 or greater. Analyses will proceed only in the treatment pairs where comparability and sufficient sample size are achieved, and not in others.

Based on the comparability analyses and sample size considerations, the risk of acute MI and the risk of stroke will be separately compared across the following three exposure contrasts: (1) erenumab-aooe vs other mAbs targeting the CGRP pathway, (2) erenumab-aooe vs select SOC migraine preventive medications (anti-epileptics), and (3) erenumab-aooe vs. onabotulinumtoxinA. For these gated analyses, we will utilize inverse probability of treatment weights to account for confounding and inverse probability of censoring weights to account for informative censoring.

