### 8.2.5 Study Follow-up

Follow-up will be evaluated in two ways. With an 'intention-to-treat' analysis, patients will be followed for all available time after they initiate a medication, irrespective of whether they discontinue the medication or not, or whether they switch to an alternate medication or not. Follow-up begins the day after the index date and ends at first occurrence of: (a) the outcome of interest, (b) disenrollment from a health plan, or (c) end of study period.

With a 'per-protocol analysis' patients are followed for as long as they are actively taking the medication of interest during the follow-up period. Follow-up begins the day after the index date and ends at first occurrence of: (a) the outcome of interest, (b) disenrollment from the health plan, (c) discontinuation of study medication, (d) switching to the alternate medication, or (e) administrative end of study. When a gap greater than the allowable gap of 30 days is encountered, discontinuation of study medication occurs at the end of the last prescription which includes the days supply (+60 day extension). Censoring due to switching will occur for the new user cohorts in this study when the following conditions are met:

- (1) For new users of erenumab-aooe, initiation of any other medication targeting the CGRP pathway (galcanezumab-gnlm, fremanezumab-vfrm, eptinezumab-jjmr, ubrogepant, rimegepant) during the follow-up period.
- (2) For new users of other mAbs targeting the CGRP pathway, initiation of erenumab-aooe, ubrogepant, or rimegepant during the follow-up period.
- (3) For new users of the SOC migraine preventive medications (anti-epileptics), initiation of any medication targeting the CGRP pathway (erenumab-aooe, galcanezumab-gnlm, fremanezumab-vfrm, eptinezumab-jjmr, ubrogepant, rimegepant) during the follow-up period.
- (4) For new users of onabotulinumtoxinA, initiation of any medication targeting the CGRP pathway (erenumab-aooe, galcanezumab-gnlm, fremanezumab-vfrm, eptinezumab-jjmr, ubrogepant, rimegepant) during the follow-up period.

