### 8.7.2 Planned Method of Analysis

#### 8.7.2.1 General Considerations

All descriptive and comparative analyses will be undertaken in the interactive Casual Studio application. Characterization of patient populations by baseline characteristics is easily accommodated by the software. In addition, the application allows for the estimation of the cumulative risk of a right censored outcome that may be subject to dependent (right) censoring. Overall estimates of risk at various time points, as well as estimates of risk stratified by medical history, demographic characteristics, and medication usage can be presented in both tabular and graphical formats.

A major challenge in observational comparative analyses is the lack of exchangeability, with baseline characteristics that may be unbalanced between study groups and potential differential drop-out across the two arms of the study. Causal Studio is a tool designed to address exchangeability in observational studies. More specifically, the application allows for the estimation of the cumulative risk of a right-censored counterfactual outcome that may be subject to dependent censoring and confounding. Causal Studio is structured as follows: (1) based on user-specified propensity score models and/or censoring models, generate inverse probability of treatment weights (IPTWs) and inverse probability of censoring weights (IPCWs); (2) provide diagnostics (eg, distribution of the propensity score, by treatment groups; and, standardized mean differences between treatment groups for categorical and continuous variables) that enable the user to assess whether the analyses should proceed to the comparative stage, and, if appropriate, (3) execute the structural (ie, weighted) model to estimate the effect of treatment on the outcome. For our purpose, we will use Causal Studio to separately compare the risk of acute MI and stroke in new users of erenumab-acoe versus new users of each of the other three new user comparator cohorts.

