### 8.7.2.4 Analysis of the Primary Endpoints

For exposition of the descriptive and comparative analytic methods below, we will focus on comparing the effect of erenumab-aooe versus other mAbs targeting the CGRP pathway on the outcome of acute MI, accounting for both confounding and differential loss to follow-up / switching / discontinuation. Note, however, that the same methods will also be applied for the outcome of stroke, for the following comparisons:

- (1) Erenumab-aooe vs other mAbs targeting the CGRP pathway (galcanezumab-gnlm, fremanezumab-vfrm, eptinezumab-jjmr)
- (2) Erenumab-aooe vs selected SOC migraine preventive medications (anti-epileptics) (topiramate, valproic acid, divalproex sodium)
- (3) Erenumab-aooe vs. onabotulinumtoxinA

The technical description of the study analyses below is ordered in the following manner. First, the naïve, unadjusted cumulative incidence (ie, risk) of acute MI is estimated in both new users of erenumab-aooe and new users of other mAbs targeting the CGRP pathway. This first step constitutes the descriptive analyses. Second, the overlap of the propensity score across treatment groups is evaluated, the mean standardized difference for all variables included in the propensity score model is assessed, and a determination is made on whether the negative control outcomes showed treatment associations within the acceptable bounds around the null. Finally, based on these comparability analyses, gated analyses in which the risk of acute MI in new users of erenumab-aooe is compared to the risk of acute MI in new users of other mAbs targeting the CGRP pathway, accounting for both confounding and differential loss to follow-up / switching / discontinuation, will be initiated.

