# Estimating the Cumulative Distribution of a Right-Censored Counterfactual Outcome, Accounting for Informative Censoring

To accommodate informative censoring due to drop-out from a health plan, switching to an alternate medication, or discontinuation of study medication, IPCWs will be estimated. Specifically, a linear-logistic model for the conditional probability of remaining uncensored  $Pr(\Delta_i=1|D_i, A_i)$ , where  $D_i$  is a vector of measured confounders of drop-out / switching / discontinuation and the outcome and  $A_i$  is a discrete random variable denoting exposure to erenumab-aooe (a=1) or other mAbs targeting the CGRP pathway (a=0) for patient i, will be fit. IP censoring weights will then be constructed as:

$$\widehat{W}_i^2 = \frac{1}{\widehat{Pr}(\Delta_i = 1 | D_i, A_i)}$$

Variables to be included in the censoring model will include demographic characteristics, medication usage, disease history, and utilization of medical resources, all of which will be included in the censoring model (see Appendix D). For new users of erenumab-aooe and other mAbs targeting the CGRP pathway, the cumulative incidence curves weighted

by inverse probability of censoring weights provide a valid estimate of the risk for acute MI at various time points, now accounting for informative censoring.

The cumulative incidence curves for acute MI, weighted by the multiple of IPTWs (ie,  $\widehat{W}_i^1$ ) and IPCWs (ie,  $\widehat{W}_i^2$ ), account for both confounding by measured covariates and informative censoring. The full estimating function for the counterfactual cumulative incidence of acute MI is then defined as:

$$\widehat{Pr}(T^a < t) = \frac{1}{n} \sum_{i=1}^{n} \frac{\Delta_i I(T_i < t) I(A_i = a)}{Pr(\Delta_i = 1 | D_i, A_i) \Pr(A_i = a | L_i)}$$

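### Per-protocol risks in the four cohorts are planned as naive curves although the protocol calls the same censoring informative, and hypertension is assigned no weights for discontinuation or switching

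*Protocol*

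**What the plan says.** **Estimator for objective 2.** The Abstract states: "The naïve, unadjusted cumulative incidence (ie, risk) of hypertension, acute MI, and stroke will be estimated in the following new user cohorts". Section 8.7.2.4 describes this as the complement of Kaplan-Meier and says of it: "This first step constitutes the descriptive analyses". It adds that "the cumulative incidence curve that is initially estimated assumes that censoring occurs at random".

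**Follow-up.** Section 8.2.5 opens with "Follow-up will be evaluated in two ways". The intention-to-treat version ignores stopping and switching. The per-protocol version ends follow-up at, among other events, "c) discontinuation of study medication, (d) switching to the alternate medication, or (e) administrative end of study". Discontinuation is dated at the end of the last supply plus a 60-day extension.

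**Where weights are assigned.** The Abstract gives the gated MI and stroke analyses "inverse probability of censoring weights to account for informative censoring". The matching subsection of 8.7.2.4, under the gated heading, begins: "To accommodate informative censoring due to drop-out from a health plan, switching to an alternate medication, or discontinuation of study medication". Section 8.7.2.4 works the methods through for acute MI and extends them to stroke; hypertension is not named.

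**Wider statements.** Section 8.7.2.2 promises censoring weights for differential loss through plan disenrollment, without restricting the outcome. Section 8.9.1.3 defines loss to follow-up broadly enough to include stopping and switching, and says time-varying covariates will be explored in the censoring models. The negative control outcomes, analysed before any decision to compare, have their risks weighted for differential loss to follow-up.

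**The concern.** One section treats the same events, stopping or switching the study drug, in two ways. In the curve that answers objective 2 they are random; in the gated comparison they are informative.

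Hypertension is not among the compared outcomes, so its per-protocol curve has no stated route to weights for these two events. MI and stroke have one only in a contrast that meets the comparability and sample-size criteria. The negative control outcomes would thus have weighted risks while a primary outcome would not.

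Hypertension is the outcome that section 6.2 says was added to the product's Warnings and Precautions. If patients at higher risk of a hypertension code stop sooner or later than others, those still under observation no longer represent the cohort, and the reported per-protocol risk drifts from the risk it is meant to estimate.

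**Working it through.** **1. The plan's own precision figures.** Table 2 uses a Wald half-width, 1.96 × √(p(1−p)/N), with the full cohort and no censoring. For N = 20 000:
- p = 0.5%: 1.96 × √(0.005 × 0.995 / 20 000) = 0.098 points (stated 0.10).
- p = 30%: 1.96 × √(0.30 × 0.70 / 20 000) = 0.635 points (stated 0.64).

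Table 2 has no row near 7.55%. The same formula there gives 0.37, 0.34 and 0.45 points for N = 20 000, 23 000 and 13 000.

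**2. Model for the naive curve.** The protocol gives no discontinuation rate, so these inputs are assumptions:
- A share p of patients (10-20%) has hypertension rate λ_H = 0.15-0.30 per year; the rest have λ_L = 0.03.
- The rest discontinue at 0.7 per year and the high-risk group at f × 0.7.
- With a 30-day first fill (assumed) plus the 60-day extension in section 8.2.5, discontinuation can censor nobody before about day 90. Earlier switching is not modelled.

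True risk: 1 − Σ p_g exp(−λ_g t).

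Naive limit: 1 − exp(−∫h), with h = Σ p_g λ_g S_g G_g / Σ p_g S_g G_g. S is freedom from hypertension and G is freedom from discontinuation.

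**3. Example (p = 20%, λ_H = 0.30, f = 2).**
- True 12-month risk: 1 − (0.2 × 0.7408 + 0.8 × 0.9704) = 7.55%.
- Without censoring, the high-risk share of patients still event-free at month 12 is 0.1482 / (0.1482 + 0.7764) = 16.0%.
- With discontinuation from day 90, multiply by exp(−1.4 × 0.7536) = 0.348 and exp(−0.7 × 0.7536) = 0.590. The share becomes 0.0516 / (0.0516 + 0.4581) = 10.1%.
- Integrating h over the year gives a naive risk of 6.92%, an error of 0.62 points.

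**4. Range at 12 months.** Errors are relative to the true risk.

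| High-risk patients stop | Error, from day 90 | Example (true 7.55%) | Error, from day 0 |
|---|---|---|---|
| 1.5 times as fast | 2-4% low | 7.22% | 4-8% low |
| 2 times as fast | 4-8% low | 6.92% | 7-14% low (6.47%) |
| 3 times as fast | 7-15% low | 6.44% | 12-25% low |
| equally fast | none | 7.55% | none |
| half as fast | 3-5% high | 7.92% | 5-9% high (8.22%) |

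Section 8.3.4 fixes hypertension at 1, 2, 3, 6 and 12 months. In the example with f = 2, the error from day 90 is essentially zero at 1 to 3 months and 0.08 points at 6 months.

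**5. The protocol's own rates.** Section 6.3 gives 3.56 hypertension events per 10 person-years, so 1 − exp(−0.356) = 29.95% at 12 months. Suppose a factor with 50% prevalence multiplies both hazards, with ratios of 1.5 to 3 for the outcome and 0.33 to 3 for stopping, and 30-70% stop by 12 months from day 0. The error then runs from −4.2 to +4.4 points, against a half-width of 0.64. These are outer values: they omit the 90-day delay, and the quoted rate may include patients with prior hypertension, whom the new-onset analysis excludes.

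In the same model the one-year error is at most 0.10 points for stroke (true 0.611%) and 0.03 for MI (true 0.183%). Table 2 gives 0.10 at 0.50% and 0.06 at 0.20%. At two years the extremes reach 0.34 and 0.10 points. Table 2 is no yardstick there, because a study period of 17 May 2018 to 31 May 2020 leaves almost nobody with two years of follow-up.

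**The case against.** The strongest defence has five parts.

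- **The curve is labelled.** The protocol calls it naive, states its assumption and says it is estimated initially. An intention-to-treat curve, not censored at stopping or switching, runs beside it. That is fair, and it confines the point to the per-protocol version. Labelling an assumption does not make it hold, though.
- **Weights may already be meant.** A reader might infer that hypertension never receives any censoring weight. The documents do not support that. Section 8.7.2.2 promises weights for disenrollment without excluding an outcome, section 8.9.1.3 speaks of censoring models in general terms, and section 8.7.2.1 says of the software that "the application allows for the estimation of the cumulative risk of a right censored outcome that may be subject to dependent (right) censoring". What stands is narrower: no section assigns the hypertension curve weights for stopping or switching, and these general statements sit uneasily with the Abstract.
- **Direction is not shown.** A reader might also infer that the per-protocol risk is understated. The protocol does not establish this. Its one link between hypertension and stopping (the third algorithm in section 8.3.4) concerns stopping after the diagnosis, when follow-up for that outcome has ended.
- **The extension softens the effect.** It does: the example error falls from 1.08 to 0.62 points.
- **Weights cannot see blood pressure.** Appendix D contains no blood pressure values, so weights correct only for measured predictors. That limits the remedy, but the protocol accepts the same limit in the gated analyses.

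A statistical analysis plan could add the weighted curves. The protocol, however, already names the estimator, its assumption and where the weights apply, so its own text needs aligning.

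**Conclusion.** The point holds for the per-protocol curves of objective 2. They rest on random discontinuation and switching, which the protocol itself treats as informative in the gated analyses. Hypertension carries the case.

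Its 12-month risk may be off in either direction, or not at all if stopping is unrelated to risk. With discontinuation possible only from about day 90, the illustrative error at a factor of 2 is 4-8% of the risk. In the example that is 0.62 points, against a half-width of about 0.34-0.45. These sizes depend on assumed rates and are not predictions.

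The effect is small at 1 to 6 months. At one year the MI and stroke errors are at or below the planned half-widths. The intention-to-treat curves are not exposed to this censoring. This is a worthwhile correction to a stated objective, not a flaw that invalidates the study, and it does not call for a comparative hypertension analysis.

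**What to change.** In section 8.7.2.4, report the per-protocol cumulative incidence of all three outcomes in all four cohorts with inverse probability of censoring weights for disenrollment, discontinuation and switching. Place it next to the naive curve, whether or not any comparison goes ahead. Use the Appendix D censoring covariates, including the utilization variables updated during follow-up. Align the Abstract and sections 8.7.2.2 and 8.9.1.3 so that they agree on which outcomes and which censoring events are weighted.

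The cost is low: the covariates are listed and section 8.7.2.1 says the software supports the method. Intervals will be somewhat wider. The report should say that the weights correct only for measured predictors, and that claims contain no blood pressure values.

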### **Comparability Analyses**

### Estimating the Propensity Score

Next, a linear-logistic model for the conditional probability of treatment,  $Pr(A_i=a|L_i)$ , where  $L_i$  is a vector of measured confounders of the exposure and the outcome, as well as risk factors for the outcome, will be fit (Brookhart et al, 2006). The conditional probability of treatment given a set of covariates is commonly referred to as the propensity score (PS).

For the first set of comparability analyses, overlap of the propensity score across treatment groups will be evaluated. Non-overlap in the PS will be addressed with trimming of subjects at the extremes of the PS distribution. In addition, the mean standardized difference for all variables included in the PS model will be estimated. An absolute mean standardized difference > 0.1 for a given confounder or risk factor for the outcome will be used as a measure of potential imbalance (Austin, 2009; Austin et al. 2007). Covariates in the propensity score model with an absolute standardized difference > 0.1 will be examined for potential inclusion in the outcome model or will be used as evidence of insufficient overlap in the distribution of baseline characteristics across treatment groups. Using PS overlap and cut points for the mean standardized difference to make decisions about cohort comparability are part of an iterative process that potentially involves trimming of subjects (because of poor overlap in the PS) and accounting for confounders in the outcome model rather than the exposure model. As such, this process provides guidance on whether cohorts are comparable and contributes additional information to the body of evidence used to determine whether comparative analyses should be initiated or not.

### Negative Control Outcome Analyses

Negative control outcome studies are designed to detect and reduce residual bias between treatment groups (Lipsitch et al, 2007, Arnold and Ercumen, 2016). Negative control outcomes are chosen that have no plausible mechanism by which they can be caused by the treatment of interest but do share unmeasured confounders (eg, lifestyle [smoking history, alcohol use], and anthropometric [BMI] variables) with the primary treatment-outcome relation. After controlling for measured confounders, any observed association between the treatment and negative control outcome can be attributed to unmeasured confounding between the groups, rather than a true causal relationship. For example, if the outcome for a comparative safety study is acute MI, the ideal negative control outcomes would share a similar confounding structure as would be hypothesized

for treatment selection (eg, erenumab-aooe vs. other mAbs targeting the CGRP pathway) and the outcome of interest (acute MI). Common outcomes used as negative controls in prior epidemiologic studies of treatments include risks of accidents or hospitalizations for trauma or injury (Dormuth et al, 2009; Brookhart et al, 2007; Jackson et al, 2006).

Selection of migraine preventive treatment is likely affected by many factors associated with a patient's prognosis that can lead to bias when comparing treatment groups in non-interventional settings. Patients initiating newer medications, such as mAbs targeting the CGRP pathway, may have more severe disease and be at higher risk for poor outcomes in comparison to patients initiating other migraine preventive therapies, such as selected SOC migraine preventive medications (anti-epileptics) or onabotulinumtoxinA . It is of interest to understand whether the incidence of clinical outcomes among patients initiating other migraine preventive medications after controlling for measured confounding factors. We will use a negative control study design to investigate this comparability of patients initiating different types of migraine preventive treatments. The results of this analysis will help inform the appropriateness of comparative safety analysis for the two CV outcomes of interest (acute MI and stroke). The negative control outcomes that may be included in the analysis are:

- o Decubitus ulcer
- o Dementia
- o Transfusions
- o Accidents
- Annual wellness visit
- Pelvic exams for cancer screening
- o Influenza vaccine use
- o Mohs surgery
- Herpes zoster vaccine
- Colon cancer screening
- Visual field tests
- Non-skin cancers
- o Fractures

We will estimate the cumulative incidence (ie, risk) and risk ratios of negative control outcomes for each treatment group comparison, controlling for measured confounders and potential differential loss to follow-up with inverse probability weights. Null

associations between the migraine preventive treatments and the negative control outcome are hypothesized. For this component of the study, an expert panel will guide selection of the final set of negative control outcomes to be used for this study.

We will use Bayesian analyses to provide evidence of treatment group comparability. The negative control effect estimates will be included as inputs (priors) for each treatment comparison, to create a posterior distribution of the bias parameter. Based on the distribution of the bias parameter, we will then estimate the probability that the bias for treatment comparison X vs. Y is less than some threshold. We will subjectively set the threshold for the risk ratio as anything between 0.91 and 1.10 as acceptable, and the Bayesian analysis will provide the posterior probability that the level of bias (unmeasured confounding) is <10% of the null. If this probability is greater than 90% we will proceed with the comparative analysis.

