#### 8.3.3 Covariate Assessment

 Table 1 below provides categorization of a set of baseline covariates that will be used to describe the study population.

Variable	Measurement	
Demographics		
Patient age (years)	Continuous, and categorized into five categories (18-24, 25-34, 35-44, 45-54, 55-64)	
Patient gender	0/1 indicator (female)	
Comorbidities		
Diabetes mellitus	0/1 indicator at study entry	
Hypercholesterolemia	0/1 indicator at study entry	
Hypertension	0/1 indicator at study entry	
Liver disease / Cirrhosis	0/1 indicator at study entry	
Depression	0/1 indicator at study entry	
Chronic Obstructive Pulmonary Disease (COPD)	0/1 indicator at study entry	
Renal Disease	0/1 indicator at study entry	
Malignancy (Other Than Skin)	0/1 indicator at study entry	
Cardiac arrhythmia	0/1 indicator at study entry	
Asthma	0/1 indicator at study entry	
Human immunodeficiency virus (HIV)	0/1 indicator at study entry	
Lupus	0/1 indicator at study entry	
Psoriasis	0/1 indicator at study entry	
Atopic dermatitis	0/1 indicator at study entry	
Rheumatoid arthritis (RA)	0/1 indicator at study entry	
Epilepsy/Seizure/Convulsions	0/1 indicator at study entry	

 Table 1. Baseline Covariates

Footnotes defined on last page of table

Page 1 of 5

Variable	Measurement
Comorbidities (continued)	
Anxiety	0/1 indicator at study entry
Depression	0/1 indicator at study entry
Peripheral Artery Disease	0/1 indicator at study entry
Venous thromboembolism	0/1 indicator at study entry
Critical limb ischemia	0/1 indicator at study entry
Myocardial Ischemia	0/1 indicator at study entry
Congestive heart failure	0/1 indicator at study entry
Acute myocardial infarction	0/1 indicator at study entry
Unstable angina	0/1 indicator at study entry
Prinzmetal angina	0/1 indicator at study entry
Other and unspecified angina pectoris	0/1 indicator at study entry
Acute atrial fibrillation	0/1 indicator at study entry
Paroxysmal atrial fibrillation	0/1 indicator at study entry
Acute ventricular fibrillation	0/1 indicator at study entry
Premature atrial contractions	0/1 indicator at study entry
Acute ventricular tachycardia	0/1 indicator at study entry
Coronary revascularization	0/1 indicator at study entry
Ischemic/hemorrhagic stroke	0/1 indicator at study entry
Sub-arachnoid stroke	0/1 indicator at study entry
Unspecified stroke	0/1 indicator at study entry
Transient ischemic attack	0/1 indicator at study entry
Other acute cerebrovascular events	0/1 indicator at study entry

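### Negative controls are screened against the treatment of interest only, and as one set for the study, so a comparator effect on a control would enter the go/no-go gate as confounding

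*Protocol*

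**What the plan says.** Section 8.7.2.4 of the protocol (Negative Control Outcome Analyses) makes five statements that bear on this point.

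- **Selection rule:** "Negative control outcomes are chosen that have no plausible mechanism by which they can be caused by the treatment of interest". The comparator is not named.
- **Interpretation:** once the recorded covariates have been adjusted for, the section holds that "any observed association between the treatment and negative control outcome can be attributed to unmeasured confounding between the groups, rather than a true causal relationship".
- **Candidates:** a list of 13 outcomes, introduced by "The negative control outcomes that may be included in the analysis are". It includes accidents, fractures and "Visual field tests".
- **Final choice:** "an expert panel will guide selection of the final set of negative control outcomes to be used for this study". The set is singular and for the study; no set per contrast is mentioned.
- **Use:** control risk ratios are estimated separately for each contrast and combined into a posterior for a bias parameter. The comparison proceeds if the probability of a risk ratio between 0.91 and 1.10 exceeds 90%. The subsection on the decision to proceed makes this a condition for both acute MI and stroke.

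The same section hypothesizes null "associations between the migraine preventive treatments and the negative control outcome are hypothesized".

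The second contrast compares erenumab with topiramate, valproic acid or divalproex sodium. Section 8.2.2.2 does not exclude epilepsy. "Epilepsy/Seizure/Convulsions" is a baseline covariate in Table 1, and Appendix D enters it in both the treatment and the censoring model.

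**The concern.** Each control risk ratio compares two active drugs. It can differ from 1 because of confounding, because erenumab affects the outcome, or because the comparator does. The selection rule removes the second cause. Nothing in the written rule removes the third, yet the interpretation assigns everything that remains to confounding.

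The gate can then err in two directions. A comparator effect on some controls can close a contrast that is in fact comparable. A comparator effect opposite in sign to real confounding can pull the pooled bias towards 1 and open a contrast that should stay closed. The second error is the more serious in a safety study, because the MI or stroke comparison would go ahead with a favourable comparability result behind it.

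The anti-epileptic contrast is the clearest case. Accidents and fractures are candidates, patients with epilepsy may enter, and Section 8.9.1.2 accepts that this cohort could be taking the drug for another indication. Weighting on baseline epilepsy balances the cohorts at entry. It does not remove an effect of the drug after initiation.

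**Working it through.** **The plan's own range.** 1/1.10 = 0.909, which rounds to 0.91. The range is therefore symmetric on the log scale apart from rounding: ln 0.91 = -0.0943 and ln 1.10 = 0.0953.

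**Inputs from the protocol.** Range 0.91 to 1.10; threshold 90%; 13 candidate controls.

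**Assumptions, because the protocol gives no values.** Equal weight on each of the 13 controls; a normal posterior for the log bias; posterior SE from 0.02 to 0.05; k controls shifted by the drug by a risk ratio RR; no true confounding unless stated.

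**Formulas.**

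centre = k × ln(RR) / 13

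P = Φ((0.0953 - centre)/SE) - Φ((-0.0943 - centre)/SE)

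**Worked case.** With k = 2 and RR = 1.5, centre = 2 × 0.4055/13 = 0.0624, a pooled risk ratio of 1.064. At SE 0.03, P = Φ(1.097) - Φ(-5.22) = 0.864, so the gate closes although there is no confounding.

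**Wrongly closed gate (no true confounding).**

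| Affected controls | RR | Pooled bias | P, SE 0.02 | P, SE 0.03 | P, SE 0.04 | P, SE 0.05 |
|---|---|---|---|---|---|---|
| 0 | any | 1.000 | 1.000 | 0.998 | 0.982 | 0.942 |
| 1 | 1.5 | 1.032 | 0.999 | 0.984 | 0.945 | 0.894 |
| 2 | 1.2 | 1.028 | 1.000 | 0.987 | 0.953 | 0.904 |
| 2 | 1.5 | 1.064 | 0.950 | 0.864 | 0.795 | 0.744 |
| 3 | 1.2 | 1.043 | 0.996 | 0.962 | 0.908 | 0.853 |
| 3 | 1.5 | 1.098 | 0.535 | 0.523 | 0.517 | 0.514 |

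If the comparator raises the control, the erenumab risk ratio falls below 1 instead. Because the range is nearly symmetric, little changes: two controls at 1/1.5 give a pooled 0.940 and P from 0.945 to 0.738 over the same SEs.

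**Sensitivity to the size of the effect.** For two controls raised by the comparator, at SE 0.04, P is 0.95, 0.91 and 0.79 for a 1.2-, 1.3- and 1.5-fold effect. The gate still opens up to about 1.3.

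**Masked bias.** Take a true bias of 1.12 (ln = 0.1133) and SE 0.03. With unaffected controls P = 0.27, and the gate correctly closes. If the comparator raises three controls 1.5-fold, centre = 0.1133 - 3 × 0.4055/13 = 0.0198, a pooled 1.02, and P = 0.99. The gate opens.

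**The case against.** The strongest reply is that nothing is settled yet. The 13 outcomes are only candidates, an expert panel guides the choice, and nothing forbids it from dropping a control for one contrast. Comparability is judged separately for each contrast. The null is hypothesized for the preventive treatments in the plural, which covers the comparators. Final lists are often left to an SAP, which is not shown here.

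Much of this stands, and it makes the harm conditional. It does not supply the missing rule. The plural null is the assumption that has to hold, not a criterion for choosing controls. The panel is given a one-sided criterion and asked for one set.

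Four stronger readings are tempting, and the documents do not support them:

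- **That the comparators do change the listed outcomes.** No section says so. For accidents and fractures with anti-epileptics it is plausible, but undocumented.
- **That epilepsy is merely recorded.** Appendix D puts it in both weighting models.
- **That any single control shifted by 10% fails the gate.** The range applies to the pooled bias parameter, not to each control.
- **That all three contrasts are affected.** No specific problem is identified for the other CGRP antibodies. For onabotulinumtoxinA, the protocol does not say that injection visits lead to wellness visits, vaccination or screening. A HCPCS code does not set it apart either, since Appendix C also lists one for fremanezumab. Those services also capture health-seeking behaviour, so removing them has a cost.

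**Conclusion.** The point holds as a defect in the selection rule, not as proof that the gate will fail. As written, Section 8.7.2.4 allows a control that the comparator can affect, and then attributes that effect to confounding in a go/no-go decision.

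The size depends on assumptions the protocol does not fix: equal weights, a normal posterior, SE 0.02 to 0.05, and the effect size. Under them, one affected control at 1.5-fold usually leaves the decision unchanged; it falls just short, at 0.894, only at SE 0.05. Two at 1.5-fold close the gate wrongly from SE 0.03 upward, but not at SE 0.02. Three close it at every SE tried. At 1.2-fold, two affected controls never close it. The masking example shows that the error can also favour proceeding. The wording should be corrected because the correction is cheap and the gate decides whether the MI and stroke comparisons are run.

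**What to change.** In Section 8.7.2.4:

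1. Require that a negative control have no plausible effect from either drug in the contrast.
2. Have the expert panel fix and document a control set for each contrast before any control results are seen, with a specific review of accidents and fractures for the anti-epileptic contrast.
3. Repeat the gate without the questionable controls as a sensitivity check, and report both results.

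Two further steps should not be mandated. Removing all visit-driven services from the onabotulinumtoxinA contrast would discard controls that reflect health-seeking behaviour. Excluding epilepsy for the gate alone would test a different cohort from the one used for MI and stroke.

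The cost is a change of wording, up to three lists instead of one, and a somewhat less precise bias estimate where controls are dropped. That loss matters: even with zero bias the gate opens only if the posterior SE is about 0.058 or less.
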